**Table 5 - AESI and search criteria**

AESI flag	Searcha criteria
Leukopenia	SMQ: Haematopoietic leukopenia
Thrombocytopenia	SMQ: Haematopoietic thrombocytopenia
Infections (Opportunistic infections, Tuberculosis)	Primary SOC: Infections and infestations (CRF checkbox: Opportunistic infections; HLT Tuberculosis infections)
Hepatic disorders	SMQ : Drug-related hepatic disorders – comprehensive search
Diverticulitis/potential GI perforations b	SMQ: Gastrointestinal perforation and HLT: Diverticulum inflammations
GI ulcerations	SMQ: Gastrointestinal ulceration
Elevation in lipids	SMQ: Dyslipidemias
Anaphylaxis	SMQ: Anaphylactic reaction
Hypersensitivity	SMQ: Hypersensitivity
[REDACTED]	[REDACTED]
[REDACTED]	[REDACTED]
[REDACTED]	[REDACTED]
[REDACTED]	[REDACTED]
[REDACTED]	[REDACTED]
[REDACTED]	[REDACTED]
Malignancy	SMQ: Malignant or unspecified tumours
Pregnancy c	CRF checkbox: Pregnancy
Overdose c	CRF checkbox: Symptomatic overdose

a All SMQs are narrow search

b These events will be further reviewed to identify cases of GI perforations

c Standard AESI applies to all Sanofi studies

#### **2.1.4.2 Deaths**

The death observation periods are per the observation periods defined above.

- Death on-study: deaths occurring during the on-study observation period
  - Death on-treatment: deaths occurring during the treatment epoch (ie, both Core and Extension treatment epoch if applicable)
  - Death during follow-up: deaths occurring during the follow-up epoch
- Death post-study: deaths occurring after the end of the study

### 2.1.4.3 Acceptability assessments (local tolerability)

The patient acceptability and local tolerability (HLT of injection site reactions) will be evaluated by the following parameters:

- Presence or absence of bruising, erythema, swelling, warmth, burning, stinging, itching, hive formation, pain, indurations, mass, discoloration, inflammation and other
  - Mild: Was able to perform normal activities, but was uncomfortable
  - Moderate: Was unable to perform some/many/most activities up to normal standards
  - Severe: Was completely unable to perform some/many/most activities

### 2.1.4.4 Laboratory safety variables

Clinical laboratory data consists of blood analysis, including hematology and clinical chemistry, and urinalysis. Clinical laboratory values will be converted to standard international units; international units will be used in all listings and tables. In addition, the lipid parameters will also be summarized in US units.

Schedule of blood samples for clinical laboratories can be found in Section 1.2 Study Flow Charts of the protocols [REDACTED]

The laboratory parameters will be classified as follows:

- Hematology
  - **Red blood cells and platelets:** hemoglobin, hematocrit, red blood cell (RBC) count and morphology (if RBC count is abnormal), platelet count
  - **White blood cells:** white blood cell (WBC) count, differential (neutrophils, lymphocytes, monocytes, eosinophils, basophils), absolute neutrophil count (ANC)
- Clinical chemistry
  - **Metabolism:** total protein, albumin
  - **Fasting lipids:** triglycerides (TG), total cholesterol, high density lipoprotein (HDL) cholesterol, low density lipoprotein (LDL) cholesterol
  - **Electrolytes:** sodium, potassium, chloride, bicarbonate, calcium, phosphate
  - **Renal function:** blood urea nitrogen (BUN), creatinine, creatinine clearance (using the equation of Schwartz for patients  $\leq 18$  years old and the equation of MDRD when patients grow to  $>18$  years old)
  - **Liver function:** alanine aminotransferase (ALT) (SGPT), aspartate aminotransferase (AST) (SGOT), alkaline phosphatase (ALP), total, conjugated, and unconjugated bilirubin, [REDACTED]

[REDACTED]

Note: Whole chemistry at baseline and week 12 (or EOT) only. At all other visits: albumin, [REDACTED] ALT, AST, ALP, and total, conjugated, and unconjugated bilirubin only.

- **Glycosylated Hemoglobin HbA1C** (screening only): levels will be measured based on the patient's medical history and investigator's judgment
- **hs-CRP and ESR**
- **Pregnancy test:** for females who have commenced menstruating, a serum test is mandatory at screening and urine tests prior to IMP exposure at other indicated visits and EOT
- **Optional: Epstein Barr Virus (EBV), Hepatitis screen, HIV** (screening only): EBV titer including IgG and IgM, hepatitis B surface antigen (HBs-Ag), hepatitis B surface antibody (HBs-Ab), hepatitis B core antibody (HBc-Ab), and hepatitis C antibody (HCV-Ab)
- **Rheumatoid Factor** (baseline only for pcJIA)

Urine samples for urinalysis will be collected at screening only:

- **Urinalysis (dipstick):** pH, specific gravity, proteins, glucose, blood, nitrates, leukocyte esterase, bilirubin

Note: If any parameter on the dipstick is abnormal, a urine sample will be sent to the central laboratory for testing. If positive for proteins, microscopic analysis will be performed by the central laboratory.

Technical formulas are described in [Section 2.5.1](#).

#### **2.1.4.5 Vital signs variables**

Vital signs include heart rate, systolic and diastolic blood pressure (SBP and DBP), temperature, height, and weight. At each visit where blood pressure is scheduled, two assessments, at least 1 minute apart, will be performed and recorded according to procedures described in the protocol.

The schedule of vital sign assessments can be found in can be found in Section 1.2 Study Flow Charts of the protocols [REDACTED]

#### **2.1.4.6 Anti-body/Serology variables**

Antinuclear antibodies/anti-ds DNA will be measured at baseline and weeks 12, 24 and then every 24 weeks up to the EOT visit.

### 2.1.5 Efficacy endpoints

The primary endpoint for these studies is PK exposure, and efficacy endpoints are secondary. Efficacy assessment will be performed as described below.

The evaluation schedule for efficacy variables can be found in Section 1.2 Study Flow Charts of the protocols [REDACTED]

Note that all efficacy evaluations up to the closeout measurement will be included for analysis unless otherwise specified. Baseline for efficacy variables is defined as the last non-missing value on or before the date of inclusion (assigned treatment). For patients who have no value on or before the inclusion date, the last non-missing value on or before the date of first IMP intake will be used as baseline.

#### 2.1.5.1 JIA ACR30 response

The definition for JIA ACR30 response [REDACTED] is  $\geq 3$  out of the 6 JIA core set variables with  $\geq 30\%$  improvement from baseline with no more than 1 of the remaining variables worsened by  $\geq 30\%$ . The core set variables include:

- **Physician global assessment of disease activity:** assessed on an anchored 100 mm horizontal visual analogue scale (VAS) where 0 is considered the best disease activity (no disease activity) and 100 the worst (most disease activity)
- **Parent or patient assessment of overall well-being:** rated on an anchored 100 mm horizontal VAS where 0 is considered the best disease activity (no disease activity) and 100 the worst (most disease activity)
- **Number of joints with active arthritis**
- **Number of joints with limited range of motion**
- **Childhood Health Assessment Questionnaire Disability Index (CHAQ-DI):** The CHAQ is a generic measure of health status in children ages 1 to 19 years of age which can be interviewer or self-administered for children  $\geq 8$  and parent/proxy-administered for children younger than 8 years of age. The questionnaire, with the past week as the time frame, is used to assess functional ability of patients with JIA in 8 domains: dressing and grooming, arising, eating, walking, hygiene, reach, grip, and activities. Each item is scored on a four point scale ranging from 0 to 3: 0 (without any difficulty), 1 (with some difficulty), 2 (with much difficult), and 3 (unable to do). An additional response of “not applicable” is available to indicate activities the patient is unable to perform because he/she is too young. The mean score of the eight domains makes up the disability index and ranges from 0 (no disability) to 3 (disabled). A CHAQ-DI score cannot be calculated validly when there are scores from less than 6 of the 8 categories. Note that items marked as not applicable are not considered in the score calculation. The disability index is supplemented with two VAS scores. The CHAQ – discomfort index rates the severity of

pain in the past week and the CHAQ health status score measures the parent or proxy's global assessment of health status, both using a 0-100 VAS scale.

- **Index of inflammation:** hs-CRP

█ [REDACTED]

### 2.1.5.2 Other secondary efficacy endpoint(s)

In addition to the assessment of responders as per the definition stated above, the other secondary efficacy endpoints for the 12-week core part are the change from baseline at week 12 in the 6 individual JIA ACR components, and JIA ACR30 response at week 12 using ESR instead of hs-CRP. Additional efficacy endpoints are listed as follows.

#### 12-week core part:

- JIA ACR 50/70/90/100 proportion responders at week 12:  $\geq 3$  out of the 6 JIA core set variables with  $\geq 50/70/90/100\%$  improvement from baseline with no more than 1 of the remaining variables worsened by  $\geq 30\%$ ; [REDACTED]
- Juvenile Arthritis Disease Activity Score-27 (JADAS-27) change from baseline at Week 12

#### Extension part:

- JIA ACR 30/50/70/90/100 proportion responders at weeks 24, 48, and every 24 weeks up to the end of the study
- JADAS-27 change from baseline at weeks 24, 48, and every 24 weeks up to the end of the study
- [REDACTED]
- █ [REDACTED]
- █ [REDACTED]

The JADAS includes 4 measures:

- Physician global assessment of disease activity (as previously defined)
- Parent or patient assessment of overall well-being (as previously defined)

- Count of joints (27) with active disease
- Index of inflammation: hs-CRP or ESR level
  - ESR normalized to a 0-10 scale according to the following formula:  
(ESR[mm/hour]-20)/10 where before making the calculation, ESR value <20 mm/hour converted to 0 and ESR value >120 mm/hour converted to 120.
  - Or hs-CRP normalized to a 0-10 scale according to the following formula:  
(CRP [mg/L] – 10)/10 where before calculation, CRP values <10 mg/L were converted to 0 and CRP values >110 mg/L were converted to 110.

The JADAS-27 will be calculated as the simple linear sum of the scores of its 4 components.

[REDACTED]

[REDACTED]

- [REDACTED]
- [REDACTED]

[REDACTED]

- [REDACTED]
- [REDACTED]
- [REDACTED]

[REDACTED]

[REDACTED]

[REDACTED]

- [REDACTED]
- [REDACTED]

[REDACTED]

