9.4.2 Juvenile arthritis disease activity Score

The JADAS includes 4 measures:

- Physician global assessment of disease activity measured on a 10-cm VAS where 0 = no activity and 10 = maximum activity
- Parent/patient global assessment of well-being, measured on a 10-cm VAS where 0 = very well and 10 = very poor
- Count of joints with active disease
- Erythrocyte sedimentation rate (ESR) normalized to a 0-10 scale according to the following formula:
 - $[\text{ESR (mm/hour)} - 20] / 10$

- Before making the calculation, ESR value <20 mm/hour converted to 0 and ESR values >120 mm/hour were converted to 120.

The JADAS will be calculated as the simple linear sum of the scores of its 4 components. (23).

The JADAS-27 includes the following joints: cervical spine, elbows, wrists, metacarpophalangeal joints (from first to third), proximal interphalangeal joints, hips, knees, and ankles. The JADAS was found to be a valid instrument for assessment of disease activity in JIA and is potentially applicable in standard clinical care, observational studies and clinical trials (23). JADAS-27 will be calculated at Visit 12 (Week 12) during the initial core treatment phase and at designated visits during the extension phase (see Section 1.2.2).

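### The JADAS-27 floor rule gives -2 (ESR) or -1 (CRP) on a component stated to run from 0 to 10, and the SAP leaves the scale of its two global VAS items unstated

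*SAP*

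**What the plan says.** SAP 2.1.5.2 (extension part) builds JADAS-27 from four items: two global assessments, an active count over 27 joints, and an inflammation item given as "Index of inflammation: hs-CRP or ESR level". The combination rule is "The JADAS-27 will be calculated as the simple linear sum of the scores of its 4 components".

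- **ESR item.** Stated range 0-10, formula (ESR-20)/10, with the rule "where before making the calculation, ESR value <20 mm/hour converted to 0 and ESR value >120 mm/hour converted to 120". Protocol 9.4.2 gives the same range, formula and truncation.
- **CRP item (SAP only).** Stated range 0-10, formula (CRP-10)/10, with "CRP values <10 mg/L were converted to 0 and CRP values >110 mg/L were converted to 110", also applied before the calculation.
- **Global items.** The SAP lists "Physician global assessment of disease activity (as previously defined") and treats the parent or patient item the same way. The definition it points back to, in SAP 2.1.5.1, is "assessed on an anchored 100 mm horizontal visual analogue scale (VAS) where 0 is considered the best disease activity" and 100 the worst. Protocol 9.4.2 instead has "Physician global assessment of disease activity measured on a 10-cm VAS where 0 = no activity and 10 = maximum activity", and puts the parent or patient item on 0-10 too.

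The score is used for "Juvenile Arthritis Disease Activity Score-27 (JADAS-27) change from baseline at Week 12" and for the same change in the extension. SAP 2.4.6.2 also explores the proportions at or below 3.8 (low disease activity) and 1.0 (inactive disease), with a Kaplan-Meier plot of time to first reaching either state.

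**The concern.** The upper limits of 120 and 110 act on the raw laboratory value and bring the item to exactly 10. The lower limit stands in the same sentence and is also applied before the formula, but it replaces the raw value with 0 rather than with the value at which the formula equals 0. A normal marker then earns negative points, and the total can fall below zero.

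Two outputs are exposed. The absolute cut-offs become easier to meet for anyone below the floor. Change from baseline gains an artificial drop in anyone who crosses the floor on treatment. Protocol 9.4.1.5 expects active regimens to lower CRP sharply, so crossings would tend to be downward and to look like benefit. For ESR that direction is an inference.

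Separately, a programmer who follows the SAP's back-reference for the global items reaches a 0-100 mm scale, and no visible SAP text rescales it. The JADAS-27 entry in SAP 2.5.2 covers only the joint count.

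**Working it through.** **Inputs.** Formulas, truncation limits and the stated 0-10 range: SAP 2.1.5.2 and, for ESR, protocol 9.4.2. Cut-offs 3.8 and 1.0: SAP 2.4.6.2. VAS scales: SAP 2.1.5.1 and protocol 9.4.2.

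**1. Upper end, which reproduces the stated 10.** ESR above 120: (120-20)/10 = 10. CRP above 110: (110-10)/10 = 10.

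**2. Lower end, stated as 0.**

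| Marker | Value used as written | Score as written | Score with raw floor at 20 or 10 |
|---|---|---|---|
| ESR 5 | 0 | (0-20)/10 = -2 | (20-20)/10 = 0 |
| ESR 19.9 | 0 | -2 | 0 |
| ESR 20 | 20 | 0 | 0 |
| CRP 9.9 | 0 | (0-10)/10 = -1 | (10-10)/10 = 0 |
| CRP 10 | 10 | 0 | 0 |

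The actual ranges are -2 to 10 and -1 to 10, with jumps of 2 points at ESR 20 and 1 point at CRP 10.

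**3. Cut-offs, with both VAS items on 0-10.** The most that the other three items may sum to is the cut-off minus the inflammation score.

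- ESR below 20: 3.8+2 = 5.8 and 1.0+2 = 3.0.
- CRP below 10: 3.8+1 = 4.8 and 1.0+1 = 2.0.

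Example with assumed values (both VAS 1.0, one active joint, ESR 10): 1.0+1.0+1-2 = 1.0, counted as inactive. With the floor corrected: 1.0+1.0+1+0 = 3.0, not inactive.

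**4. Change from baseline.**

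- ESR 21 to 19: -2-0.1 = -2.1 as written; 0-0.1 = -0.1 corrected.
- ESR 40 to 5: -2-2 = -4 as written; 0-2 = -2 corrected.
- Below the floor at both visits: the error cancels.

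The shift in a group mean is -2d for ESR or -1d for CRP, where d is the share falling below the floor minus the share rising above it. The documents do not give d. For assumed values of 0, 0.25, 0.50 and 0.75 the shift is 0, -0.5, -1.0 and -1.5 (ESR) or 0, -0.25, -0.5 and -0.75 (CRP).

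**5. VAS scale.** The maximum total is 10+10+27+10 = 57 on the protocol's scale and 100+100+27+10 = 237 if millimetres are summed. Take a child with no active joints and ESR below 20. The two VAS marks together may reach 38 mm (low) or 10 mm (inactive) on the protocol's scale with the floor corrected. Summed in mm they may reach only 3.8 and 1.0 mm with the floor corrected, or 3.8+2 = 5.8 and 1.0+2 = 3.0 mm with the floor as written.

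**The case against.** The strongest reply is that this is a wording slip. Both documents call the result a 0-10 scale, and taking the conversion to 0 as the component score restores that range. That may well be the intent. It is not what is written: both documents place the conversion before the calculation, and the paired limit of 120 or 110 works only as a raw value. One sentence would have to be read in two ways to meet its own stated range. The wording is therefore faulty, but whether it would be programmed literally is uncertain.

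The VAS point is weaker. A 100 mm line is a 10 cm line, the protocol fixes the 0-10 scoring, and summing millimetres would make the cut-offs so hard to meet that the slip should be noticed. On the other hand, protocol 9.4.2 gives no explicit division step, and its sections 9.4.1.1 and 9.4.1.2 record both items on a 100 mm VAS. A clarifying line is warranted, no more.

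A reader might infer that the low-disease and inactive-disease proportions can only be overstated. That holds only with the VAS on 0-10. If the SAP's floor and VAS text are both taken literally, the millimetre sum dominates and the proportions are understated.

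A reader might also conclude that ESR alone should be used, since protocol 9.4.2 names only ESR. The schedule does not support this. For patients switched to the selected regimen, protocol 1.2.2.2 and 10.1.9.2.1 plan JADAS-27 at Visits 101 to 106. ESR is drawn only at Visits 101 and 106, whereas hs-CRP is drawn at all six. An ESR-only score could not be computed at Visits 102 to 105. Redacted text follows the SAP definition, so the choice of marker may be stated there.

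**Conclusion.** The floor rule is wrong as written in both documents. The arithmetic is exact and needs no assumption: -2 for ESR below 20 and -1 for CRP below 10. The altered cut-offs depend on the VAS items being on 0-10, as the protocol has them. For a patient crossing the floor downward after baseline, the spurious change is -2 or -1.

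No size can be given for a mean change or a proportion. The crossing shares in the working are illustrative, and no visible entry criterion requires a raised ESR or CRP, so many patients could be below the floor throughout and add no error to the change.

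The consequence is limited. Efficacy is secondary and descriptive, no hypothesis is tested, and the cut-off proportions are exploratory. The correction is still worth making, because JADAS-27 change is a listed secondary endpoint and the fix is simple.

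**What to change.** In SAP 2.1.5.2:

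1. Convert ESR below 20 to 20, and CRP below 10 to 10, before the formula. Flooring the normalised score at 0 is equivalent.
2. State that both global VAS items enter JADAS-27 on the 0-10 scale of protocol 9.4.2, that is, mm divided by 10, and that the 3.8 and 1.0 cut-offs apply to that score.
3. Label ESR-based and CRP-based versions separately, and do not mix markers within one patient's change from baseline. For switched patients at Visits 102 to 105 only the CRP-based version is available; its baseline exists, since hs-CRP is drawn at Visit 2 (protocol 9.4.1.5).

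The cost is a few lines of SAP text and a change to the derivation, using values already scheduled for collection. Align the ESR wording in protocol 9.4.2 at the next amendment. Amendments need ethics approval (protocol section 15), and this wording does not justify one of its own.

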### 2.1.7 Immunogenicity endpoints

The ADA blood samples will be collected before injection during the same visit according to the schedules of sample collection and at or near the onset and completion of the occurrence of an SAE. Details can be found in Section 1.2 Study Flow Charts of the protocols [REDACTED]

At each sample time point, the result of an analyzed sample in the antidrug antibody (ADA) assay will be categorized as either positive or negative, and in the case of a positive result will be further characterized as either neutralizing or non-neutralizing.

**ADA positive patient** is defined as a patient with at least 1 treatment-emergent or treatment-boosted ADA positive sample during the TEAE period, where

- Treatment-emergent ADA positive patient is defined as a patient with non-positive assay (meaning negative or missing) response at baseline but with a positive assay response during the TEAE period.
- Treatment-boosted ADA positive patient is defined as a patient with a positive ADA assay response at baseline and with at least a 4-fold increase in titer compared to baseline during the TEAE period.

**ADA negative patient** is defined as a patient without a treatment-emergent or treatment-boosted ADA positive sample during the TEAE period.

A treatment-emergent positive response is further classified as persistent or transient.

- Persistent ADA Response: treatment-emergent ADA detected at 2 or more consecutive post-treatment sampling time points, where the first and last ADA positive samples are separated by a period of at least 16 weeks. Also persistent in the case where the last sample analyzed is positive, regardless of any other time points.
- Transient Response: A treatment-emergent response that is not considered persistent.

### **2.1.8 Pharmacodynamic/Pharmacogenomic endpoints**

The PD endpoints include changes from baseline at week 12 (or EOT) in IL-6 associated biomarkers (eg, serum levels of hs-CRP, IL-6, sIL-6R).

Genomic analysis will be performed in a subset of patients (separate informed consent) using a saliva sample collected at baseline (and potentially other study visits). The description of endpoints and analyses will be included in a separate document.

## **2.2 DISPOSITION OF PATIENTS**

This section describes patient disposition for both patient study status and the patient analysis populations.

Screened patients are defined as patients meeting the inclusion criteria and having a signed informed consent/assent (as applicable).

Included patients consist of all patients with a signed informed consent form who have had a treatment kit number allocated and recorded in the IVRS/IWRS database, regardless of whether the treatment kit was used.

For patient study status, the total number of patients in each of the following categories will be presented in the clinical study report using a flowchart diagram or summary table:

- Screened patients
- Screen failure patients
- Included patients
- Included but not treated patients
- Included and treated patients
- Patients completing the initial 12-week core part
- Patients completing the study treatment per protocol
- Patients not completing the study treatment period as per protocol
- Patients discontinuing study treatment by main reason for permanent treatment discontinuation
- Patients entering the extension part
- Status at last study contact

For each study disposition will be summarized by dose regimen cohort, overall and within each weight group. For all categories of patients (except for the screened), percentages will be calculated using the number of included patients as the denominator. Reasons for treatment discontinuation will also be provided by dose regimen cohort within center and/or region. At the final analysis, patient disposition in the extension part will be included.

A patient is considered lost to follow-up at the end of the study if he/she is not assessed at the last protocol planned visit and if the time from the last successful contact to the last protocol planned visit is greater than 3 days.

All critical or major deviations and inclusion and drug-dispensing irregularities will be summarized in tables giving numbers and percentages of deviations for each dose regimen cohort, overall and within each weight group.

Additionally, the analysis populations for safety, efficacy, PK, and PD will be summarized in a table by number of included patients.

- Efficacy population
- Safety population
- PK/PD/Immunogenicity population.

